5.3.2. Safety Analysis Variables

Definitions of variables for safety analysis are listed by category and alphabetically within each category.

Adverse event-related variables are listed below:

- Adverse event (AE) is defined as any untoward medical occurrence in a patient administered a pharmaceutical product, without regard to the possibility of a causal relationship.
- **AEs of special interest (AESIs)** are AEs thought to be potentially associated with the study drug or the disease under study. Therefore, aggregate AE terms for AEs typically associated with anti-angiogenesis or possibly associated with the study drug were developed.
 - Adverse events of special interest are listed in the Investigator's Brochure. The Medical Dictionary for Regulatory Activities (MedDRA $^{\mathbb{M}}$) preferred terms (PTs) that are grouped under each of the AESI terms will be provided in the compound-level safety document.
- Consolidated AEs Given the high level of granularity of the MedDRA dictionary, clinically identical or synonymous PTs reported under different terms in the database, in addition to being reported separately, will also be consolidated in a separate summary. The list of consolidated AE categories will be reported in the clinical study report.
- Serious adverse event (SAE) is any AE that results in one of the following outcomes:
 - o death
 - o initial or prolonged inpatient hospitalization
 - o a life-threatening experience (that is, immediate risk of dying)
 - o persistent or significant disability/incapacity
 - o congenital anomaly/birth defect
 - o considered significant by the investigator for any other reason

• Treatment-emergent adverse event (TEAE) is defined as any untoward medical occurrence that either occurs or worsens at any time after treatment baseline and that does not necessarily have to have a causal relationship with this treatment.

Exposure-related variables are listed below:

• Cumulative dose

- For ramucirumab, cumulative dose (mg/kg) is calculated as sum of all calculated dose levels, where calculated dose level (mg/kg) = (actual total dose (mg)) / (closest body weight (kg) prior to the treatment).
- o For erlotinib, cumulative dose (mg) is calculated as sum of all dose levels.
- o For getitinib, cumulative dose (mg) is calculated as sum of all dose levels.
- o For osimertinib, cumulative dose (mg) is calculated as sum of all dose levels.

• **Duration of treatment** (week)

For ramucirumab, duration of treatment (week) is calculated as (date of last dose
 date of first dose + 14)/7.

Note. Fourteen days is added because ramucirumab is planned to be administered every 1 cycle (14 days). Last dose stands for planned dose, regardless of whether the actual dose received is 0 or not.

• For erlotinib, duration of treatment (week) is calculated as (date of last dose - date of first dose + 1)/7, if date of last dose is collected by eCRF.

Note. If date of last dose is not collected, duration of treatment (week) is calculated as:

- (date of the discontinuation date of first dose + 1)/7, if patient discontinues ≤ 14days after the date of the last time when erlotinib is distributed; or
- (date of the last time when erlotinib is distributed* date of first dose + 14)/7, if patient discontinues > 14 days after the date of the last time when erlotinib is distributed.
- For gefitinib, duration of treatment (week) is calculated as (date of last dose date of first dose + 1)/7, if date of last dose is collected by eCRF.

Note. If date of last dose is not collected, duration of treatment (week) is calculated as:

- (date of the discontinuation date of first dose + 1)/7, if patient discontinues ≤ 14days after the date of the last time when gefitinib is distributed; or
- (date of the last time when gefitinib is distributed* date of first dose + 14)/7, if patient discontinues > 14 days after the date of the last time when gefitinib is distributed.
- For osimertinib, duration of treatment (week) is calculated as (date of last dose date of first dose + 1)/7, if date of last dose is collected by eCRF.

Note. If date of last dose is not collected, duration of treatment (week) is calculated as:

- (date of the discontinuation date of first dose + 1)/7, if patient discontinues ≤ 14days after the date of the last time when osimrtinib is distributed; or
 (date of the last time when osimrtinib is distributed* date of first dose + 14)/7, if patient discontinues > 14 days after the date of the last time when osimrtinib is distributed
- **Dose intensity** (mg/kg/week for ramucirumab or mg/week for erlotinib, gefitinib or osimertinib) is calculated as cumulative dose / component-specific duration of treatment in weeks.
- **Relative dose intensity** (%) is calculated as dose intensity / planned dose intensity * 100, where planned dose intensity = 5 mg/kg/week for ramucirumab, 150 mg/day for erlotinib, 250 mg/day for gefitinib, or 80 mg/day for osimertinib (or according to the planned dose recorded in the eCRF).
- Number of dose reductions for ramucirumab/placebo: total number of reduction steps considering the intended dose level before each infusion (as entered in the eCRF) as referenced in Table JVCY.5.2.

Table JVCY.5.2. Ramucirumab/Placebo Dose Reduction Schedule

Starting Dose	Dose Level -1	Dose Level -2	Dose Level -3
10 mg/kg	8 mg/kg	6 mg/kg	5 mg/kg
8 mg/kg	6 mg/kg	5 mg/kg	Not applicable

• Number of dose reductions for erlotinib: total number of reduction steps considering the intended dose level. Patients receiving ramucirumab or placebo plus erlotinib can have the erlotinib dose reduced if the toxicity is specifically attributable to erlotinib at the discretion of the investigator per the package insert or SPC. Patients may continue treatment with ramucirumab/placebo if they are discontinued from erlotinib. Patients should be treated following the recommendations, warnings and precautions given for erlotinib in the package insert or SPC of erlotinib.

The daily dose of erlotinib will be decreased in 50-mg decrements to a minimum dose of 50 mg daily as referenced in Table JVCY.5.3.

Table JVCY.5.3. Erlotinib Reduction Schedule

Starting dose	First Reduction	Second Reduction
150 mg/day	100 mg/day	50 mg/day

Re-escalation of erlotinib dosing is allowed at the investigator's discretion. Dose reductions must be documented within the current cycle so that treatment compliance can be determined.

- Number of dose delays for ramucirumab/placebo: Total number of treatments reported as delayed in CRF that were administered >3 days but ≤11 days beyond a scheduled infusion where treatment was not given.
 - o Dose delays for erlotinib, getifinib, and osimertinib are not captured
- Number of doses omitted (not administered) for ramucirumab/placebo: Total number of treatments reported as omitted or delayed in CRF that were administered >11 days beyond a scheduled infusion where treatment was not given.
- Number of doses omitted (not administered) for erlotinib: gefitinib, or osimertinib: Total number of doses withheld in CRF as one per omission interval. For example, if subject had to stop taking erlotinib for 5 days due to AE this is counted as one omission.

Patients receiving ramucirumab plus gefitinib can withhold gefitinib for up to 3 weeks if the toxicity is specifically attributable to gefitinib at the discretion of the investigator per the package insert. Patients may continue treatment with ramucirumab if they discontinue gefitinib. For patients whose disease has progressed in Part C Period 1, gefitinib may be continued at the discretion of the investigator, provided that the patient can still benefit from treatment. Patients on gefitinib cannot continue onto Period 2.

Patients should be treated following the recommendations, warnings, and precautions given for osimertinib in the package insert or the user guidance of osimertinib. Patients may also refer to the dose modification guidance in Table JVCY 9.4 of the JVCY Protocol Addenda 9.2.

Immunogenicity-related variables are listed below:

- Treatment-emergent antidrug antibody (TE ADA) evaluable: A patient is evaluable for TE ADA if there is at least one non-missing test result for ramucirumab ADA for each of the baseline period and the post-baseline period. All percentages are relative to the total number of subjects evaluable for TE ADA in each treatment arm.
- **TE ADA positive**: A patient evaluable for TE ADA is considered to be TE ADA+ if the subject has at least one post-baseline titer that is a 4-fold or greater increase in titer from baseline measurement (treatment-boosted). If baseline result is ADA Not Present, then the subject is TE ADA+ if there is at least one post-baseline result of ADA Present with titer >= 20 (treatment-induced).
- **TE ADA inconclusive**: A patient evaluable for TE ADA is considered TE ADA Inconclusive if 20% of the subject's post-baseline samples, drawn pre-dose, are ADA Inconclusive and all remaining post baseline samples are ADA Not Present.
- **TE ADA negative**: A patient evaluable for TE ADA is considered TE ADA- if not TE ADA+ and not TE ADA Inconclusive.

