5.15.2. Exposure

The following exposure-related variables will be reported for each part as specified:

• Exposure:

- For both ramucirumab and erlotinib duration of treatment; number of patients with dose adjustments, i.e., dose reduction, dose delay (ramucirumab only), and dose omission (Parts A and B separately)
- For both ramucirumab and gefitinib duration of treatment; number of patients with dose adjustments, i.e., dose reduction, dose delay (ramucirumab only), and dose omission (for Part C Period 1 only)
- For both ramucirumab and osimertinib duration of treatment; number of patients with dose adjustments, i.e., dose reduction, dose delay (ramucirumab only), and dose omission (for Part C Period 2 only)
- o For erlotinib: number of patients received < one week of treatment, \geq one week of treatment, \geq two weeks of treatment, \cdots , x weeks of treatment, and mean, standard deviation
- o Note: Patient is considered to have received a week of therapy after receiving at least seven doses of study drug ERLOTINIB either partial or complete.
- \circ For ramucirumab only: number of infusions received; number of patients completing < one infusion, \ge one infusion, \ge two infusions, \cdots , x infusions, and mean, standard deviation
- \circ For gefitinib: number of patients received < one week of treatment, \ge one week of treatment, \ge two weeks of treatment, \cdots , x weeks of treatment, and mean, standard deviation
- o For osimertinib: number of patients received < one week of treatment, \ge one week of treatment, \ge two weeks of treatment, \cdots , x weeks of treatment, and mean, standard deviation
- Reasons for dose adjustments and dose delays for ramucirumab, dose reductions and dose omissions (scheduling conflict, AE summarized by PT) for each

The following exposure-related variables will be reported using summary statistics (number of patients, mean, standard deviation, median, 1st and 3rd quartiles, minimum, and maximum) by treatment arm:

• Dose intensity: cumulative dose; weekly dose intensity; relative dose intensity, overall weekly dose intensity, overall relative dose intensity.

Details of study drug administration will be included in patient listings.

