5.15.8. Subgroup Analyses for Safety Evaluation

There is no subgroup analysis planned for Parts A or C.

Selected disposition and safety analyses will be performed for the following safety subgroups in Part B only:

- age (<65 years versus ≥ 65 years)
- gender (females versus males)
- race (Asian vs other)
- age (<70 years versus ≥ 70 years)
- region (East Asia versus other)
- mutation type (exon 19 versus 21)

Below is the list of the selected disposition and safety analyses for subgroup analyses for Part B and Part C:

Demographic and Other Baseline Characteristics

- Patient demographics
- Potential baseline prognostic factors for NSCLC (see Section 5.6)

Patient Disposition

- Patient disposition by investigator site and country and overall
- Reasons for treatment discontinuation

Exposure

- Summary statistics for exposure-related variables
- Dose intensity of study drugs

• Reasons for any drug adjustments

Adverse Events

- Overview of AEs
- TEAEs summarized by PT*
- CTCAE v 4.0 Grade 3 and 4 AEs*
- SAEs summarized by PT*
- AESIs by PT*
- Reasons for deaths
- AEs leading to all study treatment discontinuations summarized by PT
- AEs leading to all study drug adjustment summarized by PT

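### Relative dose intensity for erlotinib, gefitinib and osimertinib divides a weekly figure by a daily one, and the SAP states no conversion

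*SAP*

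**What the plan says.** The derivation is built up in SAP section 5.3.2, among the exposure-related variables.

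- **Cumulative dose.** "For erlotinib, cumulative dose (mg) is calculated as sum of all dose levels". Gefitinib and osimertinib are defined in the same way, in mg. Ramucirumab is in mg/kg.
- **Duration of treatment.** In weeks for every drug. For the oral drugs it is last dose date minus first dose date plus 1, divided by 7.
- **Dose intensity.** The units and formula are "mg/kg/week for ramucirumab or mg/week for erlotinib, gefitinib or osimertinib) is calculated as cumulative dose / component-specific duration of treatment in weeks".
- **Relative dose intensity, in percent.** Dose intensity over planned dose intensity, times 100, "where planned dose intensity = 5 mg/kg/week for ramucirumab, 150 mg/day for erlotinib, 250 mg/day for gefitinib, or 80 mg/day for osimertinib". A parenthesis allows another source for the denominator: "or according to the planned dose recorded in the eCRF".

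Section 5.15.2 lists what is reported by arm with summary statistics: "Dose intensity: cumulative dose; weekly dose intensity; relative dose intensity, overall weekly dose intensity, overall relative dose intensity". Section 5.15.8 repeats exposure summaries, including "Dose intensity of study drugs", in the Part B safety subgroups.

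**The concern.** A percentage should carry no unit. For ramucirumab it does not: mg/kg/week is divided by mg/kg/week. For the oral drugs the printed formula divides mg/week by mg/day. Neither section 5.3.2 nor section 5.15.2 mentions a factor of 7. The eCRF alternative gives no unit or conversion either.

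The sentence is also inconsistent within itself. Ramucirumab has already been converted from 10 mg/kg every 2 weeks to a weekly rate, while the other three drugs are left as daily doses.

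What is at stake is a reported exposure table. A program that codes the printed constants follows the SAP and gives wrong means, standard deviations, medians, quartiles, minima and maxima for the oral drugs, on a different scale from ramucirumab in the same output. A program that converts gives the right values but applies a step that the SAP does not state.

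**Working it through.** **Inputs, all from the SAP.** Ramucirumab 10 mg/kg every 2 weeks and erlotinib 150 mg daily (study description, section 1). Planned dose intensities of 5 mg/kg/week, 150, 250 and 80 mg/day, and the duration and dose-intensity formulas (section 5.3.2). Reduced erlotinib levels of 100 and 50 mg/day (Table JVCY.5.3).

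**Step 1: reproduce the ramucirumab figure.** For k infusions on schedule, cumulative dose = 10k mg/kg. Duration = ((k − 1) × 14 + 14)/7 = 2k weeks. Dose intensity = 10k/2k = 5 mg/kg/week, and relative dose intensity = 5/5 × 100 = 100%. The printed constant is right and the scale matches.

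**Step 2: apply the same formulas to an oral drug.** For D mg daily over n days, cumulative dose = D × n mg and duration = n/7 weeks. Dose intensity = D × n/(n/7) = 7D mg/week, whatever n is. Example: 84 days of erlotinib at 150 mg/day is 12600 mg over 12 weeks, or 1050 mg/week.

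**Step 3: divide by the printed constant, then by the same constant on a weekly scale.**

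| Drug and dose taken throughout | Dose intensity (mg/week) | Printed constant | Result as printed | Weekly constant | Result on matching units |
|---|---|---|---|---|---|
| Erlotinib 150 mg/day | 1050 | 150 | 700% | 1050 | 100% |
| Erlotinib 100 mg/day | 700 | 150 | 466.7% | 1050 | 66.7% |
| Erlotinib 50 mg/day | 350 | 150 | 233.3% | 1050 | 33.3% |
| Gefitinib 250 mg/day | 1750 | 250 | 700% | 1750 | 100% |
| Osimertinib 80 mg/day | 560 | 80 | 700% | 560 | 100% |

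**Step 4: the size of the error.** The ratio of the two results is 7 in every row and does not depend on length of treatment. Read the other way, a printed 100% would correspond to a true 100/7 = 14.3%.

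**Step 5: what the factor changes.** It is the same for every patient and both arms, so rankings and between-arm ratios for erlotinib are unchanged. Absolute levels, spreads and differences are all multiplied by 7.

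**The case against.** The strongest reply is that no printed number is wrong. Every quantity carries its unit, and 1050 mg/week divided by 150 mg/day is 7 days per week, which equals 1, so a reader who respects the units gets 100%. On that view the SAP only leaves a conversion unsaid. A competent programmer would supply it, and a column near 700% beside ramucirumab near 100% would be noticed.

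Much of this stands. The error is conditional on using the printed figures without conversion, and typical values would give it away. It does not remove the mismatch: a derivation rule should be executable as written, and this one gives the right percentage only if a step is added.

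Three narrower objections also have some force.

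- The SAP plans no between-arm difference or test for this variable, and Part C, where gefitinib and osimertinib are used, is single-arm. The harm is therefore to descriptive figures only.
- The eCRF is not shown, so its planned-dose field may well carry a clear unit. All that can be said is that the SAP gives no unit or conversion for it.
- The factor of exactly 7 assumes that the oral cumulative dose adds up each day's dose. That is the natural reading of a total in mg, but the SAP does not spell it out.

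**Conclusion.** The mismatch is real for all three oral drugs, and it is minor. If the printed constants are used without conversion and oral doses are summed day by day, relative dose intensity is too large by a constant factor of 7, and full dosing shows as 700%. If the units are converted, there is no error in the result.

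The effect stops at relative dose intensity and its repeats by safety subgroup in Part B. Cumulative dose, duration, weekly dose intensity, counts of dose reductions and omissions, tablet compliance (section 5.10), PFS, OS and type I error are untouched. The planned doses themselves are not in question.

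**What to change.** Put the dose-intensity and relative-dose-intensity definitions in section 5.3.2 on one time unit. Either of these will do:

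- state the oral planned dose intensity per week as 7 times the planned daily dose, which is 1050, 1750 and 560 mg/week for the doses already printed; or
- compute oral dose intensity per day for this ratio, and leave the printed daily constants as they are.

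The first keeps the weekly dose intensity that section 5.15.2 reports as the numerator. With the first option, add that a daily planned dose taken from the eCRF is multiplied by 7 as well. It would also help to say that the oral cumulative dose is summed over days.

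The cost is one line in the SAP and one constant in the derivation program. No dose, data collection or other analysis changes.

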5.14.2. Immunogenicity

For immunogenicity analyses, the number and percentage of patients with positive ramucirumab antibody response will be summarized per part. Additional efficacy or safety analyses may be performed in the subgroup of patients who are identified as treatment-emergent anti-drug antibodies (ADA) positive. The antibody response and any alteration in ramucirumab PK may

also be explored, as well as any relationship with experiencing an infusion reaction. Further exploratory analyses may be performed as appropriate.

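### TE ADA negative is a residual class: the 20% rule for Inconclusive lacks a comparator, and patients with an inconclusive baseline have no proper class, so some of unknown status are called negative

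*SAP*

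**What the plan says.** The definitions are in SAP Section 5.3.2, under the immunogenicity-related variables, which Section 3 lists among the Version 3 changes.

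- **Evaluable:** the patient has "at least one non-missing test result for ramucirumab ADA for each of the baseline period and the post-baseline period". All percentages use the evaluable patients of each arm.
- **Positive, first route:** "at least one post-baseline titer that is a 4-fold or greater increase in titer from baseline measurement (treatment-boosted").
- **Positive, second route:** "If baseline result is ADA Not Present, then the subject is TE ADA" positive with "at least one post-baseline result of ADA Present with titer >= 20 (treatment-induced").
- **Inconclusive:** the patient "is considered TE ADA Inconclusive if 20% of the subject's post-baseline samples, drawn pre-dose, are ADA Inconclusive". A second condition, on the other samples, must hold as well: "and all remaining post baseline samples are ADA Not Present".
- **Negative:** "A patient evaluable for TE ADA is considered TE ADA- if not TE ADA+ and not TE ADA Inconclusive".

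Section 5.14.2 states how the classes are used: "the number and percentage of patients with positive ramucirumab antibody response will be summarized per part". It also allows optional analyses in TE ADA positive patients and optional exploration of antibody response against PK and infusion reactions. Section 4.2 makes immunogenicity of ramucirumab a secondary objective of Part B. No other section restates or qualifies the Inconclusive rule.

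**The concern.** When negative is defined by exclusion, every gap in the other two definitions fills the negative class. There are two such gaps.

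The first is the bare 20%. Taken as an equality, it labels a patient with 1 of 5 inconclusive samples Inconclusive and a patient with 5 of 5 negative. The patient about whom less is known gets the firmer label.

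The second is the baseline. Both routes to positive need a usable baseline: a titer to multiply, or a Not Present result. A patient whose baseline assay was inconclusive offers neither, yet nothing in the evaluability wording removes that patient.

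At stake is whether the immunogenicity summary separates patients shown to be without a treatment-emergent response from patients whose status is unknown.

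**Working it through.** No stated figure in the SAP is tied to this rule, so there is none to reproduce. The check is an enumeration for the first gap and a reading of the rules against each other for the second.

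**Gap 1: the 20% without a comparator**

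Inputs: the 20% and the condition on the remaining samples, both from Section 5.3.2. The SAP does not give the ADA sampling schedule, so the number of post-baseline pre-dose samples, n, is assumed to run from 1 to 12. Let k be the number that are inconclusive (k = 1 to n), the other n − k being Not Present. Compare k/n with 20%.

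| n | k with k/n exactly 20% | smallest k for at least 20% | smallest k for more than 20% |
|---|---|---|---|
| 1 to 4 | none | 1 | 1 |
| 5 | 1 | 1 | 2 |
| 6 to 9 | none | 2 | 2 |
| 10 | 2 | 2 | 3 |
| 11, 12 | none | 3 | 3 |

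- Possible patterns: 1 + 2 + … + 12 = 78.
- Exactly 20%: 2 of 78 (1 of 5 and 2 of 10).
- At least 20%: 15 (n = 1 to 5) + 26 (n = 6 to 9) + 9 + 9 + 10 (n = 10, 11, 12) = 69 of 78.
- More than 20%: 69 − 2 = 67 of 78. It differs from at least 20% only at 1 of 5 and 2 of 10.

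The literal wording therefore sends 69 − 2 = 67 of the 69 patterns to negative. Either threshold catches every pattern that is mostly or entirely inconclusive. These are counts of possible patterns and say nothing about how many patients show them.

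**Gap 2: inconclusive baseline**

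Assume that the patient's only baseline result is ADA Inconclusive, with no titer, and that an inconclusive result is a non-missing one.

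| Baseline | Post-baseline | 4-fold route | Titer ≥ 20 route | Inconclusive rule | Class |
|---|---|---|---|---|---|
| Present, with titer | titer up 4-fold or more | met | not applicable | not needed | positive |
| Not Present | Present, titer ≥ 20 | not needed | met | not needed | positive |
| Inconclusive | at least one Present, any titer | no baseline titer | baseline is not Not Present | fails: a remaining sample is Present | negative |
| Inconclusive | all Inconclusive | no titer | fails | depends on the comparator | Inconclusive only if the 20% is a minimum |

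The third row is the gap. It does not depend on the sign before the 20%, because the Inconclusive rule fails on its other condition.

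**Effect on the reported percentage**

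Let E be the evaluable patients, P the positives and b the evaluable patients with an inconclusive baseline and nothing else usable. The positive percentage is P/E.

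- Stating the comparator changes neither P nor E.
- Requiring a conclusive baseline gives P/(E − b). P is unchanged, because none of the b patients could be positive, so the percentage is multiplied by E/(E − b).
- Assigning the third-row patients to Inconclusive leaves P/E as it is.

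The SAP does not give b.

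**The case against.** **The sign may be lost, not missing.** Symbols have dropped out of this text elsewhere: the age and duration formulas in Section 5.3 lack their minus signs, the gefitinib duration formula in Section 5.3.2 lacks the minus that the erlotinib one keeps, and the age 75 entry in the Section 3 revision history stands without a comparator. The intact 4-fold and titer criteria nearby are weak evidence against this, since one is in words and the other is typed as two ordinary characters. Many single-character signs do survive, so the cause is open. This stands. If the source PDF shows a comparator, the first gap falls; the second does not.

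**Nobody would intend an equality.** This also stands. A reader might infer that the plan chose to call wholly inconclusive patients negative. The document does not support that: a rule catching 1 of 5 but not 5 of 5 makes no sense as a design. What remains is that the text does not settle at least 20% against more than 20%.

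**The consequences are easily overstated.** A reader might infer that a negative comparison group for PK or infusion reactions is contaminated. Section 5.14.2 names no such group; it says only that these relationships may be explored. It plans a count and percentage of positive responses, and the comparator changes neither.

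**An inconclusive baseline may not count as a result.** The SAP does not say whether it is non-missing, and the baseline period may hold a second, usable result. If inconclusive were treated as missing, a patient with no other baseline result would not be evaluable and the second gap would close. But the Inconclusive definition treats ADA Inconclusive as a sample result, alongside Not Present, which favors the reading used here. A rule that needs this inference should state it.

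**Conclusion.** The point holds, as a minor one. Because negative is residual, the definitions as printed place some patients of unknown status there.

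- The missing comparator is a defect only if the source PDF also lacks it. Its effect is confined to the split between Inconclusive and negative.
- The inconclusive-baseline gap holds whatever the sign, provided that the inconclusive result is the only baseline result, carries no titer and counts as non-missing. Such a patient with a post-baseline Present result is evaluable and negative. A reader might infer that true positives are being missed; the documents do not support that, because without a baseline nobody can say whether the response is treatment-emergent. Unknown is the right description, and negative is the wrong label.

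The number of patients affected cannot be derived from the SAP and could be zero. Making a conclusive baseline a condition of evaluability could slightly change the denominator and so the positive percentage. PFS and OS are unaffected. The reasons to act are that immunogenicity is a Part B secondary objective and that the correction is very cheap.

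**What to change.** 1. Check the source PDF for a sign before the 20%. If there is none, state the threshold as a minimum, for example at least 20% of the post-baseline pre-dose samples. The sponsor should settle at least against more than, since the two differ at 1 of 5 and 2 of 10.
2. Either require a conclusive baseline result (Present with a titer, or Not Present) for TE ADA evaluability, or keep these patients evaluable and assign those with an inconclusive baseline and a post-baseline Present result to Inconclusive. The first option can change the denominator; the second leaves the positive percentage as it is.

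The cost is one or two lines in Section 5.3.2 and the matching derivation code. No additional data are needed.
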